4.3.2 Exclusion Criteria

An MID will be excluded from the trial if they present with any of the following:

- Infant ≥ 6 months of age at the time of enrolment
- Mother not breastfeeding and does not intend to initiate or reinstate breastfeeding
- Infant has a congenital condition that impacts breastfeeding e.g. cleft palate
- Mother requires medication that is contraindicated for breastfeeding
- Infant is part of a twin or multiple birth

4.4 Outcome measures include the following

Primary:

- Bristol Breastfeeding Assessment Tool (BBAT) (Appendix 7.1)

Secondary:

- Breastfeeding Self-Efficacy Scale – Short Form (BSES-SF) (Appendix 8.1)
- Visual analogue rating scales (VAS) (Appendix 9.1)
 - nipple and breast pain
 - baby's ability to latch to the breast
 - baby's ability to maintain latch to the breast
 - feeding noise

4.4.1 Bristol Breastfeeding Assessment Tool (BBAT) (Appendix 7.1)

The BBAT is a valid and reliable tool for measuring change in infant breastfeeding mechanics. [52] It was developed to measure frequently encountered postpartum breastfeeding difficulties.

The BBAT measures five aspects of breastfeeding:

- 1 Positioning
- 2 Attachment
- 3 Sucking

- 4 Swallowing
- 5 Comfort

4.4.2 Breastfeeding Self-Efficacy Scale - Short Form (BSES-SF) (Appendix 8.1)

The BSES-SF is a validated measure of change in maternal breastfeeding confidence [53]. It consists of 14 questions, each on a 5-point Likert scale with a minimum score of 0 and a maximum score of 70. The measure is set within a positive framework with each question preceded by the phrase "I can always". The higher the score, the greater the level of breastfeeding self-efficacy. A BSES-SF score of 50 is considered the threshold for identifying women at risk of ceasing exclusive breastfeeding, with a score ≤ 50 indicating an increased risk of ceasing breastfeeding. This threshold has a sensitivity of 79% and specificity of 52% and reflects those women who are likely to require care to support breastfeeding. The BSES-SF has been validated for cross-cultural adaptation. [54-56]

4.4.3 Visual Analog Scale (VAS) (Appendix 9.1)

The VAS is a valid measure of change over time. [57] A separate VAS will be used to assess four aspects of breastfeeding: nipple and breast pain experienced by the mother while feeding, level of noise made by the infant while breastfeeding, infant ability to latch to the breast, and infant ability to maintain latch. The higher the score for nipple and breast pain and noise while feeding means worse symptoms. The lower the score for ability to latch and maintain latch means more severe symptoms.

4.5 Administration of Outcome Measures

The research assistant, blinded to group allocation, will manage the administration, collection and recording of the outcome measures. All participating practitioners will be blinded to the results of the outcome measures until the data collection phase of the trial has been completed.

4.6 Data collection and collection period

Data will be collected from MIDs enrolled in the study. Data collected includes:

- Participant demographics
- Infant and maternal medical histories and breastfeeding histories
- Birth and neonatal health statistics
- Infant musculoskeletal examination findings as assessed by the initial treating osteopath
- Adverse events
- Pre- and post-BBAT scores
- Pre- and post-BSES-SF scores
- Pre- and post-VAS scores

The planned data collection period for the trial is 12 months. There is scope to extend this period if required. The need for extension will be determined by the recruitment rate.

5.0 Data Analysis

Patient demographic data will be analysed using descriptive statistics and include mean, mode, standard deviation and interquartile range for the chosen variables.

Analyses for the purpose of generating hypotheses will be conducted using the statistical software package R (version 4.1.0 and R Studio version 2022.07.1). Wilcoxon signed rank tests with continuity

correction will be used to calculate p values for changes in BBAT, BSES-SF and VAS scores pre- and post-intervention and Wilcoxon rank-sum tests will be used to determine whether BBAT and BSES-SF scores differ between control and intervention groups.

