1.7 Gaps in the research

- The effectiveness of OMT for infants with breastfeeding issues remains unclear
- Identification of the possible anatomical musculoskeletal structures involved in breastfeeding dysfunction is yet to be determined.
- The benefits of combining IBCLC with osteopathic care are unknown.

2. Aim of Research

The aim of this project is to investigate the efficacy of OMT intervention designed to address musculoskeletal dysfunction in the infant with breastfeeding difficulty.

2.1 Research questions:

This research aims to answer the following research questions:

1. Does OMT intervention deliver additional improvements in breastfeeding compared to standard care (IBCLC) in infants with breastfeeding difficulty?
2. Does OMT intervention deliver additional improvements in breastfeeding mechanical function compared to standard care (IBCLC) in infants with breastfeeding difficulty?
3. Does OMT intervention deliver additional improvements in maternal breastfeeding confidence compared to standard care (IBCLC) in infants with breastfeeding difficulty?

2.2 Research Hypotheses:

This study aims to test the following research hypotheses:

1. OMT intervention to the infant improves breastfeeding more than standard care (IBCLC) in infants with breastfeeding difficulty.
2. OMT intervention to the infant improves breastfeeding mechanical function more than standard care (IBCLC) in infants with breastfeeding difficulty.

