4.3 Selection methods – inclusion/exclusion criteria

4.3.1 Inclusion criteria

To be eligible to enrol in the trial, an MID must meet the following criteria:

- Mother must have read the information sheet (Appendix 5.1) and signed the consent form (Appendix 6.1).
- MID must have an intake BBAT score of ≤ 5
- Mother must be 18 years of age or older
- In order to provide informed consent, the mother requires a certain level of proficiency in English. If she is not sufficiently proficient in English, the mother can use the Federal Government's Telephone Interpreter Service. This can be organised by the CI at short notice. <https://www.tisnational.gov.au/Our-services/>, <https://www.vic.gov.au/interpreters-and-translations>. Given prior notice, the CI can organise the translation service to be available at the time of the appointments with the IBCLC and Osteopaths. Alternatively, the mother can provide her own support person to help with translation.
- Mother must self-identify as having difficulty breastfeeding
- Mother must be breastfeeding, attempting to breastfeed, or wishing to re-establish breastfeeding
- Infant must be < 6 months of age at the time of enrolment
- Infant gestation at birth must be ≥ 37 weeks

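### Section 5.0 gives the four VAS secondary outcomes only a pre/post test, with no comparison between arms

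*Protocol*

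**What the plan says.** Section 5.0 of the protocol assigns tests to outcomes by name. Wilcoxon signed-rank tests "will be used to calculate p values for changes in BBAT, BSES-SF and VAS scores pre- and post-intervention". The same sentence then says that "Wilcoxon rank-sum tests will be used to determine whether BBAT and BSES-SF scores differ between control and intervention groups". VAS is in the first list and absent from the second. No other section of the protocol gives a between-arm analysis of VAS.

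VAS is a listed secondary outcome in section 4.4, and section 4.4.3 makes clear that it is several outcomes: "A separate VAS will be used to assess four aspects of breastfeeding". With BBAT and BSES-SF, that makes six outcome measures, of which four are VAS scales.

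The research questions in section 2.1 are comparative. The first reads "Does OMT intervention deliver additional improvements in breastfeeding compared to standard care (IBCLC) in infants with breastfeeding difficulty", and the second asks the same of mechanical function: "Does OMT intervention deliver additional improvements in breastfeeding mechanical function compared to standard care (IBCLC) in infants with breastfeeding difficulty".

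Section 5.0 also qualifies its own status: "Analyses for the purpose of generating hypotheses will be conducted using the statistical software package R".

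**The concern.** The trial randomises so that OMT added to lactation care can be compared with lactation care alone. A pre/post test makes no use of the randomised control. Under section 4.1.4 both arms receive lactation-consultant sessions and calls over four weeks. The infants also grow older, and dyads enroll while the mother is reporting difficulty. Improvement in pain, latch and noise is therefore plausible in both arms without any effect of OMT, and a small pre/post p value would not separate these explanations.

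This matters for the VAS scales in particular because section 4.1.2 puts forward latching, maintaining latch and maternal pain as the problems that osteopathic techniques may relieve. Three of the four VAS scales measure those problems, yet the plan tests none of them against control.

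Two things are at stake. First, the report would have no planned estimate or test of an OMT effect on these outcomes, and a comparison added after the data are seen would look post hoc. Second, if the signed-rank tests are run separately in each arm, a significant result in one arm and not in the other can be misread as a difference between arms.

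**Working it through.** **1. Tests by outcome, from section 5.0**

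| Outcome | Pre/post signed-rank | Between-arm rank-sum |
|---|---|---|
| BBAT (primary) | yes | yes |
| BSES-SF (secondary) | yes | yes |
| VAS pain, latch, maintaining latch, noise (secondary) | yes | **not named** |

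This table carries the finding. The rest only illustrates what a pre/post test can and cannot show.

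**2. The plan's group size**

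Inputs from section 7.0: SD 2, MCID 1.5, alpha 0.05 (taken as two-sided, since the protocol does not say), power 80%, drop-out 10%.

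- Normal approximation: n = 2 × (1.96 + 0.842)² × (2/1.5)² ≈ 27.9, so 28 per arm.
- t-test: 28.9, so 29 per arm.
- Allowing for the rank-sum efficiency of 3/π: 29 ÷ 0.955 ≈ 30.4, so 31 per arm and 62 in total.
- Drop-out: 62 ÷ 0.90 ≈ 68.9, so 69, or 70 for equal arms.

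The protocol's 31, 62 and 70 are reproduced by this route, though it does not say how it reached 31. The illustration uses 31 per arm.

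**3. What a pre/post test shows when OMT adds nothing**

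Assumptions: changes are normal with SD 1 and the same mean d in both arms, so d is the common improvement in SDs of change. There are 31 per arm, tests are two-sided at 0.05, the signed-rank test has a continuity correction, and 4,000 trials were simulated for each d. The values of d are assumed, because the protocol gives no VAS SD, MCID or expected change.

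| d | One arm's signed-rank p < 0.05 | Exactly one arm p < 0.05 | Both arms pooled, signed-rank p < 0.05 | Rank-sum between arms p < 0.05 |
|---|---|---|---|---|
| 0 | 4% | 9% | 5% | 5% |
| 0.2 | 18% | 29% | 33% | 5% |
| 0.36 | 47% | 49% | 78% | 5% |
| 0.5 | 75% | 37% | 97% | 5% |
| 0.75 | 97% | 5% | 100% | 5% |

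Check on the third column: with independent arms, the chance that exactly one is significant is 2p(1 − p). For d = 0.5, 2 × 0.754 × 0.246 = 0.37. For d = 0.36, 2 × 0.471 × 0.529 = 0.50, against 0.49 simulated. By symmetry, about half of these one-arm results favour OMT.

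The signed-rank columns respond to the shared improvement. Only the rank-sum column responds to a difference between arms, and it stays near its nominal level throughout.

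**4. Can the existing sample carry a VAS comparison?**

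Assume a standardised VAS difference of 0.75, borrowed from the BBAT ratio 1.5/2. Simulated rank-sum power per scale is then 0.76 with 28 per arm, 0.80 with 31 and 0.85 with 35, before any multiplicity adjustment. The borrowed ratio is an assumption, not a protocol figure.

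**The case against.** The strongest reply is that little is at risk. The primary outcome and the BSES-SF do have a between-arm test, and the sample size rests on the BBAT. The question on mechanical function is served by the BBAT and the one on confidence by the BSES-SF. No research question names VAS. The BBAT itself scores attachment and comfort, so constructs close to latch and pain are compared within the primary outcome. The analyses are labelled hypothesis generating, and a statistical analysis plan may hold more detail.

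Most of this stands as a limit on importance, but none of it supplies the missing comparison. A hypothesis about OMT and pain or latch still needs the control arm. Nor is this merely detail left for later: section 5.0 names VAS for one test and leaves it out of the other.

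Several stronger readings are tempting, and the documents do not support them:

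- *The trial cannot answer its question.* This holds only for the planned VAS analysis. VAS is collected in both randomised arms, and the primary comparison is intact.
- *The report will claim a significant gain in the OMT arm.* The protocol does not say how pre/post results will be interpreted. It also does not say whether the tests are run per arm or pooled. If pooled, a result in exactly one arm cannot arise.
- *Regression to the mean from the entry rule gives a known VAS improvement.* The rule "MID must have an intake BBAT score of ≤ 5" selects on the BBAT. It would carry over to VAS only through a correlation that the protocol does not give.
- *All pre/post tests must go.* For BBAT and BSES-SF they accompany a between-arm test and can stand as supplementary.

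**Conclusion.** The point holds in limited form. As written, four of the six outcome measures, all secondary, receive only an uncontrolled pre/post test, which cannot show added benefit of OMT whether run per arm or pooled. The conclusion rests on the wording of section 5.0 and needs no numerical assumption.

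The percentages are illustrative. They depend on an assumed common improvement of 0.2 to 0.75 SD of change, 31 evaluable dyads per arm, normal changes and, for the one-arm figures, separate tests in each arm. The range of about 5% to 49% for exactly one significant arm should be cited as a range. No single value in it is supported by the protocol.

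**What to change.** In section 5.0, add the four VAS scales to the between-arm comparison and label them secondary. The smallest change is to name VAS alongside BBAT and BSES-SF in the rank-sum sentence. Preferable, though not forced by the documents, is a baseline-adjusted difference between arms with a 95% CI for each scale at weeks 4 and 8. State that pre/post VAS p values will not be used as evidence of an OMT effect, and say whether the signed-rank tests are per arm or pooled.

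The cost is a little more analysis and four more secondary tests. If the four were independent and unadjusted at 0.05, the chance of at least one false positive would be 1 − 0.95⁴ ≈ 0.19, so they should be reported as secondary and read accordingly. No new data are needed, since section 4.1.4 already schedules the outcome measures at baseline and weeks 4 and 8, and N does not change. Making the change before the data are analysed keeps the VAS comparison prespecified.

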PROTOCOL DOCUMENT FOR THE BREASTFEEDING OSTEOPATHIC MANUAL THERAPY STUDY (BROMS)

[name]
[name]
Adjunct Associate [name]
Associate [name]

Protocol for the Breastfeeding Osteopathic Manual Therapy Study

This Project Description provides the scientific and academic background and context for the research project 'Breastfeeding Osteopathic Manual Therapy Study (*BROMS*)'.

Summary:

This study is a two-armed, multi-centre, pragmatic, randomised clinical trial designed to examine the effect of osteopathic care (OMT) on breastfeeding dyads experiencing breastfeeding difficulty. The trial will be conducted in two stages: preliminary and full. Both stages have the same design.

The preliminary stage will pilot the design at a single clinic in Melbourne by recruiting 16 mother-infant dyads (MIDs) experiencing breastfeeding difficulty. The full stage will extend the pilot to multiple clinics across Melbourne and Canberra (See Appendix 1.1 – Clinic Consent Form).

Participants in both stages will be randomly allocated to one of two groups: international board-certified lactation consultant (IBCLC) - Standard care (Control) or IBCLC plus osteopathic intervention (OMT) (Experimental). The full stage will continue the pilot stage and see a further 54 MIDs (total N=70) experiencing breastfeeding difficulty randomly allocated to the same two groups. Recruitment for this stage will be from osteopathic clinics, maternal health centres and breastfeeding drop-in centres across metropolitan Melbourne and Canberra.

Each participant will undergo 4 weeks of intervention with a follow-up phone call one-month post-intervention.

The primary outcome of the study is change in infant breastfeeding function as measured by the Bristol Breastfeeding Assessment Tool (BBAT).

Secondary outcomes include maternal breastfeeding confidence, as measured by the Breastfeeding Self-efficacy Scale – Short form (BSES-SF) and changes in breastfeeding symptoms such as maternal breastfeeding-related pain, infant ability to latch and maintain latch to the breast and feeding noise at the breast measured using a series of visual analogue scales (VAS).

1. Study details

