4.1.4 Trial design

All participants will require a pre-screen appointment to assess their eligibility to join the trial.

All participants will receive a maximum of two IBCLC face-to-face sessions and two IBCLC telehealth calls over a 4-week period. In addition to this, the IBCLC group will receive up to two additional telehealth consultations if required whereas the IBCLC + OMT group will receive up to three OMT consultations.

Outcome measures will be administered at baseline and again at weeks 4 and 8. At 8 weeks, all participants will receive a follow-up phone call/email from the trial coordinator, which will gather information on the breastfeeding status of the MID.

[figure not shown]

Figure 1: Flow chart

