7.0 Sample Size and Statistical Power Calculation

An *a priori* sample size calculation was performed using existing data on the BBAT. With 2 Groups, a standard deviation of 2, a minimum clinically important difference (MCID) of 1.5, [52] an Alpha of 0.05 and power set at 80%, the minimum group size was calculated to be 31, giving a total sample size of 62. Allowing for a 10% drop-out rate means a total sample size of 70 is required.

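### Section 5.0 labels the analyses hypothesis-generating, compares the arms on BBAT scores without the baseline, and reserves change, the stated primary outcome, for paired pre/post tests

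*Protocol*

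**What the plan says.** - **Primary outcome.** The protocol summary states: "The primary outcome of the study is change in infant breastfeeding function", measured by the BBAT.
- **Purpose.** Section 2.2 opens: "This study aims to test the following research hypotheses". Both hypotheses there are comparative: OMT improves feeding more than IBCLC care does.
- **Sizing.** Section 7.0 uses two groups, SD 2, "a minimum clinically important difference (MCID) of 1.5", alpha 0.05 and 80% power. It arrives at 31 per group, 62 in total, and 70 after 10% drop-out.
- **Status of the analyses.** Section 5.0 begins its inferential part: "Analyses for the purpose of generating hypotheses will be conducted using the statistical software package R". No other inferential analysis of BBAT is described.
- **Tests.** For the signed-rank tests, Section 5.0 says that the continuity "correction will be used to calculate p values for changes in BBAT, BSES-SF and VAS scores pre- and post-intervention". For the comparison of arms it says "Wilcoxon rank-sum tests will be used to determine whether BBAT and BSES-SF scores differ between control and intervention groups". No covariate is named, and the VAS scales get no between-arm test.
- **Data available.** Section 4.1.4: "Outcome measures will be administered at baseline and again at weeks 4 and 8". Section 4.3.1 makes an intake BBAT of 5 or less an entry condition, so every enrolled dyad has a baseline value.

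**The concern.** Two things in the text conflict, and a third is a missed opportunity.

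First, a trial that is sized at a set alpha and power to test a directional claim should have one confirmatory comparison. Section 5.0 puts its only comparison of the arms under an exploratory label. On the protocol's own wording, a positive BBAT result could be set aside as hypothesis-generating.

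Second, the sentence on testing attaches change to the signed-rank tests and plain scores to the rank-sum test. A signed-rank test asks whether BBAT moved from before to after. In infants enrolled because they feed poorly, that can happen in both arms without any effect of OMT. If one arm reaches significance and the other does not, that is still no test of the difference between them.

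Third, the baseline of the primary outcome is already collected but plays no part in the between-arm comparison.

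**Working it through.** **Inputs.** From Section 7.0: difference 1.5, SD 2, alpha 0.05, power 80%. From Section 4.2: 1:1 allocation. Assumed here: a two-sided test (the protocol does not say); SD 2 as the SD of the score (Section 7.0 does not say whether it is of the score or of the change); approximately normal scores; baseline-outcome correlation r from 0.3 to 0.5, with 0.7 as an outer value.

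**1. The plan's own figure.** Standardised difference d = 1.5/2 = 0.75.
- Normal approximation: 2 × ((1.960 + 0.842)/0.75)² = 27.9, so 28 per arm.
- Noncentral t: 29 per arm (80.1%); at 31 per arm, 82.8%.
- Rank-sum test with its efficiency under normality, 3/π = 0.955: 31 × 0.955 = 29.6 effective dyads per arm, giving 81.0%. With 30 per arm it is 79.6%, so 31 is the smallest adequate number.
- Drop-out: 31/0.9 = 34.4, so 35 per arm, 70 in total.

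The stated 31 and 70 are therefore reproduced as a rank-sum sample size. (Noether's formula gives about 32 per arm, so the match depends slightly on the approximation.)

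**2. Using the baseline.** The residual SD after adjustment is 2 × √(1 − r²). Noncentral t power at 31 per arm:

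| r | Residual SD | Power, baseline-adjusted | Power, rank-sum on post score |
|---|---|---|---|
| 0.3 | 1.908 | 86% | 81% |
| 0.4 | 1.833 | 89% | 81% |
| 0.5 | 1.732 | 92% | 81% |
| 0.7 | 1.428 | 98% | 81% |

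About 2 points of each gain come from moving from ranks to means under normality (81.0% to 82.8%). The rest comes from the baseline. A simulation of 4,000 trials at each of r = 0.3, 0.5 and 0.7 gave 81% for the rank-sum throughout and 86%, 92% and 98% for the adjusted analysis.

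**3. If scores was meant as change scores.** The SD of change is √(2² + s² − 2 × r × 2 × s), where s is the baseline SD. With s = 2 this is 2 × √(2(1 − r)), and the rank-sum power is 67% at r = 0.3, 74% at 0.4, 81% at 0.5 and 96% at 0.7. Entry at BBAT 5 or less truncates the baseline, so s may well be below 2. For s between 1.7 and 1.3, a t-test on change has 75% to 82% power at r = 0.3 and 81% to 86% at r = 0.4. Change can thus do worse or better than the post score, depending on two quantities the protocol does not give.

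**4. An estimate to set against 1.5.** The 95% CI half-width of an unadjusted mean difference at 31 per arm is 2.000 × 2 × √(2/31) = 1.02 BBAT points. That is narrow enough to be informative beside a difference of 1.5.

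**The case against.** The strongest reply is that the planned test works. Under randomisation, an unadjusted comparison of post-intervention scores is a valid test of the arm effect. Chance imbalance at baseline is already covered by its alpha, and 31 per arm delivers the intended power. All of this stands. A reader might infer from the unused baseline that the trial is underpowered or the test biased; the documents support neither.

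It can also be said that covariates, estimates and intervals are usually left to a statistical analysis plan, which may exist. That is fair, and their absence alone would be no finding. But the protocol does not stay silent here: it fixes the test, what each test is applied to, and the status of the analyses, and those statements conflict with its own summary and Sections 2.2 and 7.0.

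The authors may have meant change scores in both halves of the sentence. That is possible. The wording does not say so, and step 3 shows that the choice affects power.

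Finally, a reader might infer that a rank-sum analysis can never be held against 1.5. That goes too far. Section 5.0 promises only p values and whether scores differ, but a Hodges-Lehmann shift with a confidence interval in BBAT points could accompany the test, and nothing in the protocol rules it out.

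**Conclusion.** The point holds in two parts of different weight.

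The contradiction needs correcting and rests on no assumption. Section 5.0 calls hypothesis-generating what Sections 2.2 and 7.0 set up as a powered hypothesis test. Read literally, it also tests the primary outcome, change in BBAT, only by paired pre/post tests that contain no contrast between arms.

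Baseline adjustment is a recommendation: it improves on a test that already reaches its target. Its size is about 5, 8 or 11 percentage points of power at 31 per arm for r = 0.3, 0.4 or 0.5, given a score SD of 2 and normality. The restricted entry range may lower r, so the smaller gain is plausible.

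A reader might also infer that analysing raw change must cost power. That holds only for particular combinations of correlation and baseline SD, neither of which the protocol reports.

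**What to change.** In Section 5.0, state that the primary confirmatory analysis compares week-4 BBAT between the randomised arms, adjusted for baseline BBAT (ANCOVA), and reports the adjusted mean difference with its 95% CI, read against 1.5, at a two-sided 0.05 level. With the baseline as covariate, the arm effect is the same whether the response is the week-4 score or the change from baseline, so this also honours the stated primary outcome.

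Keep the rank-sum test as a sensitivity analysis for a bounded score, with a Hodges-Lehmann shift and CI; a proportional-odds model with baseline would also serve. Describe the signed-rank pre/post tests as descriptive. Apply the hypothesis-generating label only to secondary and exploratory analyses.

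The cost is a protocol wording change, mirrored in any analysis plan, made before outcome data are compared by arm (Section 19 foresees an interim analysis at 28 participants). It needs no new data and no larger sample.
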